11.1.2 Per Protocol

The per protocol analysis set (PP) consists of subjects in the ITT analysis set that did not experience any of the following major protocol deviations:

- Violations of inclusion/exclusion criteria for study
- Non-compliance (less than 18 hours of ActiGraph wear-time in a day) of more than two days during the first or twelfth week after enrollment

The PP analysis set will only be used, if different than the ITT analysis set, in a secondary analysis of the primary effectiveness endpoint assessing the sensitivity to the choice of analysis set.

11.2 Control of Systematic Bias

Several measures have been incorporated into the study design to minimize study including, but not limited to, the following:

- A multi-center trial minimizes investigator, center, or subject bias
- Consecutively eligible subjects should be enrolled into the study
- This Statistical Analysis Plan specifies appropriate statistical methodology to minimize bias
- Subjects are randomized to one of two arms, POC plus SOC for LTOT (treatment) or SOC for LTOT alone (control), which minimizes systematic bias in the subject treatment
- Standardized and validated questionnaires are used to collect data

11.3 Pooling Across Centers

All data will be pooled across centers for all analyses. Centers may be compared using summary statistics. An assessment of the appropriateness of pooling may be conducted using a linear regression model with the primary effectiveness endpoint as the outcome and center, treatment arm, and the interaction between the center and treatment arm as predictors.

11.4 Descriptive Statistics

Descriptive statistics will be presented for subject demographics, study disposition, screening information, ActiGraph device compliance, assessment results, and for any other characteristics data collected during the study.

11.5 Handling of Missing Data

A sensitivity analysis will be performed on the primary effectiveness endpoint to assess the effect of missing data. The results using the following imputation methods will be evaluated and compared to the results from the primary analysis:

- Missing week 12 follow-up visit PAL values are imputed with the most recent set of 7 consecutive days with available data from the second half of the 12-week follow-up period (i.e., weeks 7-12)
- Missing week 12 follow-up visit PAL values are imputed with the most recent set of 7 consecutive days with available data from the last quarter of the 12-week follow-up period (i.e., weeks 10-12)

11.6 Data Summaries

Unless otherwise stated, data will be summarized as followed:

- Continuous variables will be summarized with the count, mean, standard deviation, median, and range. Hypothesis testing will use the t-test (or Wilcoxon rank-sum test).
- Categorical variables will be summarized with counts and percentages. Hypothesis testing will
 use the chi-squared test (or Fisher exact test).
- Level of significance (α) for statistical testing will be 0.05 and two-sided.

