10.3 Visit 1: Randomization and Baseline Visit

After a potential study patient has 1) completed the initial informed consent process and signed the study-specific informed consent form, 2) successfully completed the baseline 6MWT, and 3) been determined to meet all inclusion criteria and none of the exclusion criteria, the patient will be randomized in a 1:1 ratio to either SOC long-term oxygen therapy only (control arm) or SOC long-term oxygen therapy plus a POC (treatment arm). Randomization will be stratified by site and will be implemented via small permuted blocks. Randomization assignments will be assigned through the electronic study database and will be obtained by trained site personnel. A patient is considered enrolled at the time of randomization. Patients will be given all study devices relevant to their study arm assignment and will receive training on all devices at the baseline visit. Patients will be instructed to contact their site study staff with any questions pertaining to the study.

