14.3 Analysis of Secondary and Exploratory Endpoints

The full list of all secondary and exploratory endpoints can be found in Section 5.3. The mean changes from baseline in continuous secondary and other endpoints will be compared between treatment groups via independent samples t-tests, or a non-parametric equivalent as appropriate. General Linear Modeling will be used to assess the impact of potentially influential covariates.

For comparisons of categorical variables, a chi-square test (if appropriate) or Fisher's exact test will be used. Standard logistic regression will also be fit to these endpoints to include center effects and relevant covariates.

For certain variables associated with only one treatment arm, such as POC usage, summaries and estimation, including 95% confidence intervals, may be provided, with no formal hypothesis test performed.

The frequencies of each individual type of adverse event will be summarized along with a 95% exact binomial upper confidence bound. Adverse events, including UADEs, will also be summarized based upon seriousness, severity and relation to the procedure and the device. Individual adverse events will be listed for both groups, including time to event and resolution.

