3.1 Study Design/Overview

This is a post-approval, randomized, unblinded, multicenter, parallel group study with 12 weeks of followup. The study will be performed at up to twenty (20) centers in the United States. Up to 190 subjects (95 per treatment arm) will be enrolled in the study.

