3.3.4 Randomization

Subjects will be randomized according to the pre-specified randomization schedule following the confirmation of enrollment eligibility. Subjects will be randomized to either the treatment or control arm in a 1:1 ratio. The randomization will be based on random, permuted blocks and stratified by center. Randomization will continue sequentially regardless of a subject not being treated according to their randomization assignment.

4 Study Objectives

This study is designed to evaluate the effect of using a POC combined with SOC long-term oxygen therapy versus SOC long-term oxygen therapy alone on the physical activity level of subjects with COPD requiring long-term oxygen therapy. This study will also assess the effect on oxygen usage, quality of life, hospitalizations, and death and the safety of the device.

5 Endpoints

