5.4 Adverse Events

All adverse events will be recorded and reported.

6 Analysis of Primary Effectiveness Endpoint

The primary effectiveness endpoint analysis evaluates the difference in the mean change in PAL from baseline to the week 12 follow-up visit between the treatment and control arms. For accuracy, only wear-filtered ActiGraph data will be used in the analysis. The baseline PAL uses the average TEE and average SEE values during the first week of the study and the week 12 follow-up visit PAL uses the average values from the twelfth week of the study. Only subjects with available baseline and week 12 follow-up visit PAL values will be included in this analysis.

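### The primary test leaves out centre, the randomisation stratum; if PAL change differs between centres, the test is conservative and some power is lost

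*SAP*

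**What the plan says.** Both documents stratify the allocation. SAP 3.3.4 states "The randomization will be based on random, permuted blocks and stratified by center", and protocol 10.3 states "Randomization will be stratified by site and will be implemented via small permuted blocks". SAP 3.1 sets the scale: "The study will be performed at up to twenty (20) centers in the United States".

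SAP section 6 says that the primary analysis "evaluates the difference in the mean change in PAL from baseline to the week 12 follow-up visit between the treatment and control arms" but names no test. The default for continuous variables in SAP 11.6 therefore governs: "Hypothesis testing will use the t-test (or Wilcoxon rank-sum test").

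SAP 11.3 adds "All data will be pooled across centers for all analyses". Its one provision for a model with centre in the primary endpoint is optional and serves another purpose: "An assessment of the appropriateness of pooling may be conducted using a linear regression model with the primary effectiveness endpoint as the outcome". Protocol 14.4 makes that pooling check mandatory and allows small centres to be combined into super-centres. The only SAP model that adjusts a treatment comparison for centre is the Cox model for exploratory endpoint 1 (SAP section 8).

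**The concern.** Blocking within centre keeps the arms nearly balanced in every centre, so differences between centres largely cancel from the arm comparison. A two-sample t-test does not use this. It leaves between-centre variation in its error term, so if centres differ in mean PAL change, its standard error describes a less precise comparison than the one that was made. The confidence interval is then too wide and the nominal 5% test runs below 5%.

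At stake is precision on the primary endpoint. SAP section 2 reports closure at 109 of 190 planned subjects, so little can be spared. As the plan stands, an exploratory endpoint is adjusted for the stratification factor and the primary endpoint is not.

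**Working it through.** **Inputs from the documents.** Difference 0.1, SD 0.22 in each arm, two-sided 5%, at least 80% power, 20% attrition (SAP 6.2); 109 enrolled (SAP section 2); up to 20 centres (SAP 3.1); 1:1 allocation (SAP 3.3.4).

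**Inputs assumed.** The ICC, meaning the share of the variance of PAL change that lies between centres, varied from 0 to 0.20; blocks of 4; unequal centre sizes; dropout at random. The documents give no between-centre variance, no numerical block size and no count of centres that enrolled. In PAL units the between-centre SD is 0.22 × √ICC: 0.049, 0.070 and 0.085 at ICC 0.05, 0.10 and 0.15.

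**Step 1: the plan's own figure.** An unadjusted two-sample t-test (noncentral t) has 79.5% power at 76 per arm and 80.03% at 77. The stated 77 per arm reproduces, and it was computed for the same unadjusted comparison that the SAP specifies. The standard error at 77 per arm is 0.22 × √(2/77) = 0.0355.

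**Step 2: the standard error under ideal balance.** With perfect balance in every centre, the true variance of the arm difference is 2 × 0.22² × (1 − ICC)/n, while the t-test estimates about 2 × 0.22²/n. The standard error is too large by the factor 1/√(1 − ICC), and type I error is approximately 2 × [1 − Φ(1.96/√(1 − ICC))].

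| ICC | SE too large by | Type I error |
|---|---|---|
| 0 | 0% | 5.0% |
| 0.05 | 2.6% | 4.4% |
| 0.10 | 5.4% | 3.9% |
| 0.15 | 8.5% | 3.4% |

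**Step 3: power at the size reached.** 109 × 0.8 / 2 = 43.6 evaluable per arm, where the t-test has 55.5% power. Under ideal balance, removing the centre variance would raise this to about 58%, 60% and 62% at ICC 0.05, 0.10 and 0.15. Dropout and incomplete blocks disturb the balance, so these are upper limits. Simulated power with 109 enrolled, 20% dropout and 20 centres was:

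| ICC | t-test | Random intercept | Difference (points) |
|---|---|---|---|
| 0 | 54.2% | 54.8% | +0.6 |
| 0.05 | 55.3% | 56.6% | +1.3 |
| 0.10 | 55.4% | 58.6% | +3.2 |
| 0.15 | 55.4% | 60.6% | +5.2 |

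The random-intercept model had type I error of 4.6% to 5.4%; that of the t-test fell to 3.8% at ICC 0.15 and 3.3% at 0.20. A second simulation (3,000 runs per cell) gave differences of +0.7, +1.4, +3.2 and +4.9 at the same four ICCs. Monte Carlo error on a single power is about √(0.55 × 0.45/3000) = 0.9 points, so the result at ICC 0 should be read as no loss, not as a gain.

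**Step 4: other ways to include centre** (same setting).

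- One fixed effect per centre (6,000 runs per cell): 55.7% falls to 51.1% at ICC 0, 55.9% to 53.2% at 0.05 and 55.5% to 54.6% at 0.10; at 0.20 it rises from 56.8% to 61.5%. Other runs put the loss at 3.7 to 3.8 points at ICC 0 and 2.3 at 0.05.
- Small centres grouped, then fixed effects (3,000 runs): 55.1% to 54.0% at ICC 0, 54.3% to 53.7% at 0.05, 55.6% to 56.4% at 0.10 and 55.4% to 57.5% at 0.15.

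**Step 5: the planned size.** With 190 enrolled, 20% dropout and 20 centres, t-test against random intercept gave 80.0% and 80.1% at ICC 0, 79.0% and 81.9% at 0.10, and 81.8% and 86.6% at 0.20.

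The calculations cover the t-test; the Wilcoxon alternative, which also ignores centre, was not simulated.

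**The case against.** The strongest reply is that the loss is hypothetical. The endpoint is a within-patient change, which already removes stable centre differences in the level of PAL, and nothing in the documents shows that centres differ in change. At ICC 0 the t-test is right. This stands, and it is why the point is conditional.

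Second, adjustment can do harm: with up to 20 centres and 109 patients, one fixed effect per centre loses power at low ICC. This also stands, but it counts against that model only. The random intercept showed no loss in any setting simulated.

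Third, the omission does not inflate type I error, and the sample size was derived for this same test. Early closure matters far more: power is about 65% if all 109 are evaluable and about 55% with 20% attrition, against 80% planned. All of this is correct. It limits the importance of the point without removing it.

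A reader might also infer that the SAP removed a centre-adjusted primary analysis which the protocol had planned. The documents do not support that. Protocol 14.3 says "General Linear Modeling will be used to assess the impact of potentially influential covariates", but that section covers secondary and exploratory endpoints and the sentence concerns covariates; its logistic models with centre are for categorical endpoints. For the primary endpoint, the protocol's only model with centre is the pooling check in 14.4, which the SAP keeps as optional.

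**Conclusion.** The point holds in conditional form. The primary test omits the factor on which randomisation was stratified. If centres differ in mean PAL change, the test is conservative; if they do not, it is correct. Under assumed ICCs of 0.05 to 0.15 at the size reached, a random-intercept model would recover about 1 to 5 points of power over about 55% and keep type I error near its nominal level, at essentially no cost if the ICC is zero. These figures also rest on the assumed 20 centres, blocks of 4, unequal centre sizes and random dropout.

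Two stronger readings fail. It cannot be said that the standard error is certainly too large, because the documents give no between-centre variance. Nor can the full gain of the ideal-balance formula (55.5% to 58%, 60% or 62%) be claimed, because it assumes perfect balance within every centre.

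**What to change.** In SAP section 6, name the primary test: the arm coefficient with its 95% confidence interval from a linear model of PAL change on arm, with centre as a random intercept. State the estimation method and how the degrees of freedom are obtained. Keep the t-test as a sensitivity analysis. Use the same model for continuous secondary endpoints 1, 2, 3 and 6.

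Do not fit one fixed effect per centre. Fixed effects for super-centres, which protocol 14.4 already permits, are an acceptable but weaker alternative; the grouping rule should then be written down. SAP version 1.0 is dated 18 August 2020, after the study closed on 30 April 2020, so the number and size of the enrolling centres can be stated. Report the estimated between-centre variance with the result.

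The cost is SAP wording and a slightly more complex model. No additional data are needed.

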11.7 Statistical Software

The statistical software package SAS® 9.4 or later will be used for all the data derivations, summarization, data listings and statistical analyses. Additional statistical software may be used for graphics or validation purposes as appropriate.

12 Version History

Version	Date	Description of Changes
1.0	18 Aug 2020	Initial description of analyses
